9. Provide a summary of the statistical methods, data analysis, or data interpretation planned for this study. Factors for determining the proposed sample size (e.g., power) should be stated.

Preliminary Analyses

Baseline characteristics will be summarized by randomized treatment group with standardized differences between treatment groups used to assess the balance of patient characteristics between the two groups. Univariate summaries will also be performed at baseline and follow-up for the primary and secondary outcome variables. If quantitative outcome variables exhibit substantial skewness, transformations may be sought to better approximate normality.

Primary Analysis of Headache Days

The primary analysis of the efficacy of the thin-film intervention will be conducted as an analysis of covariance comparing the proportion of days during the 12 week follow-up period recorded as headache days between the thin-film treatment group and the tinted glasses group, using the proportion of headache days during the 4-week baseline as a covariate. The null hypothesis of no treatment effect on headache frequency will be rejected if the 2-sided p-value corresponding to the treatment effect is smaller than 0.05.

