In a secondary analysis, generalized estimating equations (GEE) will be applied to a generalized linear model in which the probability of reporting a headache day during the treatment period is related to a) the baseline frequency of headache days, b) the randomized treatment group, c) week of follow-up, defined as a categorical variable, and d) the interaction of the randomized treatment group with follow-up week. This analysis will be used to characterize the treatment effect over different portions of the follow-up period. A binary outcome model with a logistic link function will be used. A compound symmetry working covariance matrix will be applied and robust standard errors will be used for statistical inferences. The analysis will provide estimates of the odds ratio (with associated 95% confidence intervals and p-values) for reporting a headache day between the two treatment groups obtained separately for each follow-up month. If the interaction between the randomized treatment group and week of follow-up is not statistically significant at the $\alpha=0.05$ level, an overall estimate of the odds ratio for reporting a day with severe headache between the two treatment groups will be provided under a reduced model which excludes the randomized treatment group by follow-up week interaction. For reporting purposes, we will

also provide ratios of the probabilities for reporting headache days using a marginal means approach, with bootstrap resampling used to estimate 95% confidence intervals and p-values.

Analysis of HIT-6

The main secondary analysis of the HIT-6 Total Score will be performed using a linear mixed effects model for a normally distributed outcome. The mixed effects model will relate the mean HIT-6 scores at weeks 4, 8, 12, and 16 of treatment to a) the baseline (week 0) HIT-6 score, b) the randomized treatment group, c) the follow-up visit, defined as a categorical variable, and d) the interaction of the randomized treatment group with follow-up visit. An unstructured covariance model will be used to account for repeat observations over the three follow-up assessments. The main contrast to evaluate the treatment effect will compare the mean HIT-6 scores over the 4, 8, 12 and 16 week visits; additional exploratory contrasts will compare the HIT-6 scores at weeks 4, 8, 12, and 16 individually.

Sample Size and Power

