Outcomes defined as proportions of days meeting designated criteria based on diary information. Analyses of secondary and exploratory outcomes defined by proportions of days during the follow-up period that satisfy designated conditions will be carried out using the same GEE approach that was described for the secondary analysis of the proportion of headache-free days. Thus, for each outcome, we will estimate the treatment effect separately during each of the four follow-up months as well as the overall effect across all 4 follow-up months.

Numeric outcomes. Descriptive summaries and graphical displays using histograms will provide numeric outcome variables at baseline and over the respective follow-up assessments, by treatment group. Transformations may be sought to better approximate normality for outcomes exhibiting substantial skewness. Numeric secondary and exploratory outcomes that are assessed at baseline and the week 4, week 8, week 12 and week 16 follow-up visits will be analyzed using the linear mixed effects modeling approach described for the HIT-6 score.

Multiple comparisons. Both the primary and the main secondary outcomes will be compared between the randomized groups using a 2-sided α -level of 0.05. Additional secondary and exploratory outcomes will also be compared between the treatment groups using a 2-sided α level of 0.05, without adjustment for multiple comparisons. However, all results from these analyses will be interpreted as exploratory and will take into account the risk of Type 1 errors resulting from multiple hypothesis tests.

Missing Data. The computation of the % of headache days will include only those days with non-missing headache diary information. This analysis will remain approximately unbiased as long as the days on which headache status is recorded in the diaries are independent of actual headache status. The analysis of the HIT-6, which is based on a linear mixed effects model, will be approximately unbiased so long as the pattern of missing data is missing at random, meaning that the probability that an outcome measurement is missing may depend on the values of other non-missing measurements, but not on the value of the missing measurement itself. If the fraction of missing HIT-6 scores exceeds 10% at any given follow-up visit, multiple imputation will also be applied prior to the analysis of the main secondary HIT-6 outcome.

Interim Analysis.

No formal interim analyses for efficacy will be performed.

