In our previous study, a majority of subjects had statistically significant reductions in the headaches. If successful, these spectacle coatings may be the first FDA-approved treatment for migraine that specifically addresses light sensitivity. Based on our previous study, it is expected that most subjects in both arms of the study will experience at least some reduction in their light sensitivity. Results from this study will help other migraine patients determine if spectacle tints and/or thin-films might be beneficial to them.

3. Are there any costs to the participants from participation in research?

Yes No

If yes, specify:

4. Is there any compensation to the participants?

Yes No

a. If yes, answer the following:

Specify overall amount:

Subjects who complete the entire study will choose to either keep their study glasses or receive a check for \$100.

Subjects who complete the first 4 weeks of the study, but who are withdrawn because they no longer meet inclusion/exclusion criteria at the 4-week visit will receive a check for \$25.

b. Specify when participants will be paid (e.g. at each visit, at end of study, etc.):

As above.

c. If applicable, please specify payment by visit or other time interval (e.g. \$10 per visit, etc.):

Not applicable

d. If applicable, explain plan for prorating payments if participant does not complete the study:

Payments will not be prorated except as stipulated, above.

IRB_00086498

Created: 9/19/2015 4:57 PM

PI: [name]

Submitted: 3/29/2016

Title: Spectacle Tints and Thin-Films to Reduce Headache Frequency
in Patients with Migraine

7. HIPAA and the Covered Entity

1. **Does this study involve Protected Health Information (PHI) or de-identified health information?**

Yes No

a. **Select the method(s) of authorization that will be used:**

(Consent and) Authorization Document

Waiver or Alteration of Authorization

b. **Will PHI be disclosed outside the Covered Entity?**

Yes No

To whom?

FDA

And for what purposes?

The FDA may request an audit of the data if they are used to request a labeling indication as a treatment for migraine.

Does this study involve any of the following:

2. **The investigational use of a drug?**

Yes No

3. **The investigational use of a medical device?**

Yes No

4. **Is this an investigator-initiated drug or device trial lead by the Principal Investigator?**

Yes No

5. **Exposure to radioisotopes or ionizing radiation?**

Yes No

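### The plan tests headache days and HIT-6 each at two-sided 0.05 and gives no rule for HIT-6 if the primary fails; one sentence fixing the order would close the gap at no cost in sample size

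*Combined protocol and SAP*

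**What the plan says.** All of the statistical text is in section 4 (Study Information), item 9.

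- **Primary.** Headache days are analysed by ANCOVA. The null hypothesis is to be "rejected if the 2-sided p-value corresponding to the treatment effect is smaller than 0.05".
- **Main secondary.** Under Analysis of HIT-6: "The main secondary analysis of the HIT-6 Total Score will be performed using a linear mixed effects model". One contrast is singled out: "The main contrast to evaluate the treatment effect will compare the mean HIT-6 scores over the 4, 8, 12 and 16 week visits". The contrasts at individual visits are called exploratory.
- **Error rates.** The Multiple comparisons paragraph has two tiers. First: "Both the primary and the main secondary outcomes will be compared between the randomized groups using a 2-sided" level of 0.05. Second: "Additional secondary and exploratory outcomes will also be compared between the treatment groups", also at 0.05 and without adjustment. The caution comes after the second tier: "However, all results from these analyses will be interpreted as exploratory".
- **Not stated.** Item 9 gives no testing order, no split of alpha and no target for the error rate across the two first-tier tests. It plans no formal interim efficacy analysis, so no alpha is spent there.

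Outside the statistical section, section 7, item 1b says that the FDA may audit the data "if they are used to request a labeling indication as a treatment for migraine".

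**The concern.** The caution about exploratory interpretation follows the sentence on additional outcomes, so its natural reach is that second tier. If it reached back to the first tier, it would make the primary exploratory too, which conflicts with the primary's explicit rejection rule. HIT-6 therefore sits above the exploratory outcomes, at the full 0.05, and is not made to depend on the primary.

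The case that matters is a primary that misses significance while HIT-6 reaches it. The plan does not say whether that result is a finding of superiority or only supportive. The stated purpose in section 1, item 6 is to learn whether one lens treatment is superior, and it names no outcome. The status of a lone HIT-6 result would then be settled after the data are seen. A possible labeling request makes it more useful to settle this beforehand.

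**Working it through.** **1. The plan's own figure.** Inputs from Sample Size and Power: SD 18.6 points, baseline to follow-up correlation 0.55, difference 7.8 points, 80% power, two-sided 0.05, 10% loss.

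- Residual SD = 18.6 × √(1 − 0.55²) = 15.53.
- n per arm = 2 × 15.53² × (1.960 + 0.842)² / 7.8² = 62.3, rounded up to 63.
- With 10% loss: 63 / 0.90 = 70 per arm, 140 in total.

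This matches the plan. Power with 63 evaluable per arm is 80.5% (79.8% with the noncentral t). The calculation covers headache days only; no power is given for HIT-6.

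**2. Tests in the family.** There are two: the primary treatment effect and the one HIT-6 main contrast. Each is at two-sided 0.05.

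**3. Chance of at least one false rejection when both nulls are true.** With Z1 and Z2 standard normal with correlation ρ:

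P(at least one) = 1 − P(|Z1| < 1.96 and |Z2| < 1.96).

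For ρ = 0 this is 1 − 0.95² = 9.75%. The other rows use the bivariate normal distribution. The last column subtracts the primary's own 5%.

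| Assumed ρ | At least one false rejection | HIT-6 alone |
|---|---|---|
| 0 | 9.75% | 4.75% |
| 0.5 | 9.1% | 4.1% |
| 0.7 | 8.3% | 3.3% |
| 0.8 | 7.8% | 2.8% |
| 0.9 | 7.0% | 2.0% |
| 0.99 | 5.7% | 0.7% |

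The lower limit is 5% (tests fully correlated). The upper bound under any dependence is 0.05 + 0.05 = 10%. If only one of the two nulls is true, the chance of a false rejection is 5%, so the excess arises only when both are true.

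**4. With a fixed sequence.** HIT-6 can be claimed only after the primary rejects.

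- If the primary null is true, any false claim requires the primary to reject, which has probability 5%.
- If the primary null is false, the only possible false claim is on HIT-6, with probability at most 5%.

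The error rate is therefore at most 5% in every case. The primary is still tested at 0.05, so 140 subjects and about 80% power are unchanged.

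**5. For comparison, an equal split at 0.025 each.** The error rate is 1 − 0.975² = 4.94% if the tests are independent. Primary power with 63 evaluable per arm falls to 71.8%. Restoring 80% needs 76 evaluable per arm; 76 / 0.90 rounds up to 85 per arm, or 170 randomized.

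**The case against.** The strongest reply is that the plan already ranks the outcomes. The study title concerns headache frequency. The only explicit rejection rule is for headache frequency. The sample size rests on headache days alone, and HIT-6 is called secondary. Testing a secondary outcome at 0.05 sets a nominal level; it does not by itself open a second route to success. This stands in part. An order of importance is stated, and the primary conclusion keeps its 5% error rate. What is missing is the rule that turns rank into a decision when the primary fails.

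A reader might infer that HIT-6 is a second confirmatory or co-primary endpoint. The documents never call it either, and never say that superiority may be declared on it alone.

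The labeling sentence is weak evidence. It is conditional, it answers a question about disclosure of health information, and it names no endpoint. It shows that regulatory use is contemplated, not that a claim on HIT-6 alone is.

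Finally, item 9 asks for a summary of methods, and section 8, item 2 mentions a protocol document that site investigators sign. A hierarchy could be written there. That limits the finding to the text reviewed; it does not fill the gap in that text.

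**Conclusion.** The point holds as an omission. The reviewed text contradicts no promise of its own, because it never undertakes to hold the error rate at 5% across the two tests. The sample size is sound and is not affected.

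The size is a chance of between 5% and 10% of at least one false claim. It rests on three conditions: both nulls are true, a positive HIT-6 result alone would be treated as a claim, and the correlation between the two test statistics is as assumed. It would be tempting to say that the rate is 8–10% rather than 5%. The documents do not support that as a fact: they give no correlation between headache days and HIT-6, the figure drops below 8% by a correlation of 0.8, and 5% across both tests was never a stated target.

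The change is worth making because it is cheap and settles the interpretation in advance, not because the primary analysis is at risk.

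**What to change.** In the Multiple comparisons paragraph, before the groups are compared, state that:

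1. the primary is tested at two-sided 0.05;
2. the HIT-6 main contrast is tested as confirmatory at two-sided 0.05 only if the primary is significant;
3. otherwise HIT-6 is reported as exploratory, like the additional outcomes.

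The gated contrast also needs correcting. As written it averages weeks 4, 8, 12 and 16. Table 1 and the Visit 2 description have the glasses first received at week 4, and the questionnaire is listed there before the spectacles. The week 4 score is therefore a pre-treatment value. The same HIT-6 paragraph refers to three follow-up assessments, and exploratory outcome b lists weeks 8, 12 and 16. Define the main contrast over weeks 8, 12 and 16. If the four visits were weighted equally, a constant difference d after treatment starts would appear as (0 + 3d)/4 = 0.75d.

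The cost is a sentence or two in Multiple comparisons and a corrected visit list under Analysis of HIT-6. The number randomized stays at 140 and the primary keeps its alpha and power. The one loss is that no confirmatory HIT-6 claim can be made if the primary fails. If HIT-6 is meant only as supportive, saying so also leaves a single confirmatory test at 5%.

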The person obtaining consent will ask potential subjects if they'd like more time to think about participation or if they'd like the opportunity to discuss participation with family or friends.

6. **Will a legally authorized representative (LAR) be used?**

Yes No

7. **Will a language other than English be used to obtain consent?**

Yes No

8. **Are you requesting that documentation of informed consent be waived by the IRB (a consent process in place, but no documentation of consent, e.g. questionnaire cover letter, web-based consent, consent without signature, etc.)?**

Yes No

If yes, complete the following:

- a. **Explain why the waiver of consent documentation is being requested.**
- b. **Justification for the waiver is one of the following:**
There are no items to display

IRB_00086498

Created: 9/19/2015 4:57 PM

PI: [name]

Submitted: 3/29/2016

Title: Spectacle Tints and Thin-Films to Reduce Headache Frequency
in Patients with Migraine

5. Data Monitoring Plan

- 1. Privacy Protections:** Privacy refers to persons and to their interest in controlling access of others to themselves. Privacy can be defined in terms of having control over the extent, timing and circumstances of sharing oneself (physically, behaviorally, or intellectually) with others. **What precautions will be used to ensure subject privacy is protected?**

Select all that apply:

The research intervention is conducted in a private place

Discussing the study with participants individually instead of in front of a group

The collection of information about participants is limited to the amount necessary to achieve the aims of the research, so that no unneeded information is being collected

Other or additional details (specify):

- 2. Confidentiality Precautions:** Confidentiality is an extension of the concept of privacy; it refers to the subject's understanding of, and agreement to, the ways identifiable information will be stored and shared. Identifiable information can be printed information, electronic information or visual information such as photographs. **What precautions will be used to maintain the confidentiality of identifiable information?**

Select all that apply:

Storing research data on password protected computers or in locked cabinets or offices

Participant identifiers will be stored separately from the coded, participant data

Other or additional details (specify):

- 3. Will photos, audio recordings, or video recordings, or medical images of participants be made during the study?**

Yes No

If yes, describe the recording/images and what will become of them after creation (e.g., shown at scientific meetings, stored in the medical/research record, transcribed, erased, etc.):

- 4. How will study data and documentation be monitored throughout the study?**

Select all that apply:

Periodic review and confirmation of participant eligibility

Periodic review of informed consent documentation

Periodic review of the transfer/transcription of data from the original source to the research record

Confirmation that all appropriate information has been reported to the sponsor, oversight agencies (such as the FDA), and/or IRB

Other additional details (specify):

- 5. Who will be the primary monitor of the study data and documentation?**

Select all that apply:

Study Monitor or Contract Research Organization (CRO)

Other or additional details (specify):

6. How often is study data and documentation monitoring planned (e.g., monthly, twice a year, annually, after N participants are enrolled, etc.)?

Study data and documentation monitoring will take place at each site after 5 subjects have been enrolled, after 10 subjects have been enrolled, after 15 subjects have been enrolled, after 20 subjects have been enrolled, and at closeout.

IRB_00086498

Created: 9/19/2015 4:57 PM

PI: [name]

Submitted: 3/29/2016

Title: Spectacle Tints and Thin-Films to Reduce Headache Frequency in Patients with Migraine

Safety Monitoring Plan

1. Describe the safety monitoring entity for this study:

a. Select all that apply:

Principal Investigator

Please specify:

b. Describe the expertise and affiliation of the individual(s) selected above who will monitor the study:

[name] is a board-certified ophthalmologist and University of Utah physician.

2. Describe the data and events that will be monitored and reviewed (e.g., vital signs, safety blood labs, depression scales, neurological exams, types of adverse events, etc.):

Serious adverse events, defined as events related to the Trial that result in a participant being injured, being evaluated in an emergency room, admitted to a hospital, or death, shall be reported to the Sponsor by phone within 24 hours of the CRO's knowledge of the event.

Serious adverse events that are deemed by the Site Investigator not to be related to the Trial will be reported to the Sponsor on a quarterly basis, by written report from the CRO.

Adverse events that are not serious will be reported to the Sponsor on a quarterly basis, by written report from the CRO.

3. Describe the types of reports that will be produced by the monitoring entity (e.g., safety, study progress, interim analysis, etc.):

Safety reports will be produced each quarter. There will be no study progress reports or interim analyses.

4. Describe the specific triggers or stopping rules for the study:

a. Under what conditions will a participant be withdrawn from the study?

A subject can always voluntarily withdraw.

At the 4-week visit, a member of the research team will review the diary entries for the past 4 weeks. Subjects who have a headache frequency less than 50% will be withdrawn. Subjects who have a headache frequency of 100% will be withdrawn.

The site investigators or principal investigator may withdraw a participant for the following reasons:

- 1) Failure to attend scheduled follow-up appointments
- 2) Failure to complete diaries or other study instruments
- 3) Failure to comply with study guidelines

b. Under what conditions will the study be modified or stopped?

There are no plans to modify the study. A similar previous study was completed at the University (IRB #47263) and no adverse events occurred.

There are no plans to stop the study. As it is minimal risk, conditions for stopping the study have not been established.

The Sponsor reserves the right to temporarily suspend or prematurely discontinue this study either at a single site, multiple sites, or at all sites at any time for reasons including, but not limited to, safety or ethical issues, inaccurate or incomplete data recording, noncompliance, or unsatisfactory enrollment with respect to quality or quantity. If the study is prematurely terminated or suspended, the Sponsor (or its representative) will inform the investigators/institutions, and the regulatory authority(ies) of the termination or suspension and the reason(s) for the termination or suspension, in accordance with applicable regulatory requirement(s). The IRB will also be informed and provided with reason(s) for the termination or suspension by the Sponsor or by the investigator/institution, as specified by the applicable regulatory requirement(s). In addition, arrangements will be made for the return of all unused investigational products and other material in accordance with the Sponsor's procedures for the study.

5. How often will the data and events be reviewed by the monitoring entity (e.g., after every 5 submits, monthly, quarterly, twice a year, etc.)?

Data and events will be monitored annually

IRB_00086498

Created: 9/19/2015 4:57 PM

PI: [name]

Submitted: 3/29/2016

Title: Spectacle Tints and Thin-Films to Reduce Headache Frequency in Patients with Migraine

6. Risks and Benefits

1. Describe the reasonable foreseeable risks or discomforts to the participants:

Because a similar study was conducted at the University without any adverse events, we do not anticipate any significant risks in the current study.

Subjects who don't already wear glasses may find wearing glasses uncomfortable. The PI has made every attempt to choose glasses that are lightweight and comfortable. The PI has also arranged for each site to have a companion optical shop available to adjust the frames for maximum comfort.

There is a risk that participants will not experience any improvement in their headaches. None of the subjects in our previous study reported an exacerbation of their headaches during the study.

There is a risk of loss of confidentiality.

2. Describe the potential benefits to society AND to participants (do not include compensation):

In our previous study, a majority of subjects had statistically significant reductions in the headaches. If successful, these spectacle coatings may be the first FDA-approved treatment for migraine that specifically addresses light sensitivity. Based on our previous study, it is expected that most subjects in both arms of the study will experience at least some reduction in their light sensitivity. Results from this study will help other migraine patients determine if spectacle tints and/or thin-films might be beneficial to them.

3. Are there any costs to the participants from participation in research?

Yes No

If yes, specify:

4. Is there any compensation to the participants?

Yes No

a. If yes, answer the following:

Specify overall amount:

Subjects who complete the entire study will choose to either keep their study glasses or receive a check for \$100.

Subjects who complete the first 4 weeks of the study, but who are withdrawn because they no longer meet inclusion/exclusion criteria at the 4-week visit will receive a check for \$25.

b. Specify when participants will be paid (e.g. at each visit, at end of study, etc.):

As above.

c. If applicable, please specify payment by visit or other time interval (e.g. \$10 per visit, etc.):

Not applicable

d. If applicable, explain plan for prorating payments if participant does not complete the study:

Payments will not be prorated except as stipulated, above.

IRB_00086498

Created: 9/19/2015 4:57 PM

PI: [name]

Submitted: 3/29/2016

Title: Spectacle Tints and Thin-Films to Reduce Headache Frequency
in Patients with Migraine

7. HIPAA and the Covered Entity

1. **Does this study involve Protected Health Information (PHI) or de-identified health information?**

Yes No

a. **Select the method(s) of authorization that will be used:**

(Consent and) Authorization Document

Waiver or Alteration of Authorization

b. **Will PHI be disclosed outside the Covered Entity?**

Yes No

To whom?

FDA

And for what purposes?

The FDA may request an audit of the data if they are used to request a labeling indication as a treatment for migraine.

Does this study involve any of the following:

2. **The investigational use of a drug?**

Yes No

3. **The investigational use of a medical device?**

Yes No

4. **Is this an investigator-initiated drug or device trial lead by the Principal Investigator?**

Yes No

5. **Exposure to radioisotopes or ionizing radiation?**

Yes No

6. **A Humanitarian Device Exemption (HDE)?**

Yes No

7. **Genetic testing and/or analysis of genetic data?**

Yes No

8. **Creating or sending data and/or samples to a repository to be saved for future research uses?**

Yes No

9. **Are you introducing recombinant or synthetic nucleic acids (such as viral vectors, plasmids, or oligonucleotides, or cells containing recombinant or synthetic nucleic acids)**

or human pathogens (viruses, bacteria, etc.) into human research participants or collecting samples (blood, tissue, cells, etc) from human participants for research purposes?

Yes No

10. **Does this study involve any of the following?**

- **Cancer Patients**
- **Cancer Hypothesis**
- **Cancer risk reduction**
- **Cancer prevention**

Yes No

11. **Any component of the Center for Clinical and Translational Science (CCTS)?**

Yes No

The Clinical Services Core (CSC)?

Yes No

IRB_00086498

Created: 9/19/2015 4:57 PM

PI: [name]

Submitted: 3/29/2016

Title: Spectacle Tints and Thin-Films to Reduce Headache Frequency
in Patients with Migraine

Request for Waiver or Alteration of Authorization

Request for Waiver of Authorization for **Recruitment Only**

This option must only be used if you are reviewing PHI in order to identify eligible participants BEFORE approaching them to obtain consent and authorization. All other waiver requests must be entered below.

Waiver of Authorization for Recruitment Requested

Other Requests for Waivers of Authorization:

- *Click "Add" below to add a new waiver request to this application.*
- *Click the waiver name link to edit a waiver that has already been created.*
- *To delete a waiver request, contact the IRB.*

Date Created	Type of Request	Purpose of Waiver Request
--------------	-----------------	---------------------------

There are no items to display

IRB_00086498

Created: 9/19/2015 4:57 PM

PI: [name]

Submitted: 3/29/2016

Title: Spectacle Tints and Thin-Films to Reduce Headache Frequency in Patients with Migraine

Request for Waiver or Alteration of Authorization

Request for Waiver of Authorization for Recruitment Only

The PI must agree to the terms of this waiver request as described on this page. When the PI uses the "Submit" activity to submit the application for IRB review, a checkbox to accept the terms will be available in the "Submit" activity window.

This waiver request includes justification for waivers of consent for recruitment only, according to 45 CFR 46.116(d).

Terms for the Waiver of Authorization:

- The purpose of this waiver of authorization is to allow for the use of PHI in order to identify and recruit individuals who may be eligible to participate in the specific research described in this IRB application. The waiver of authorization is necessary to accommodate this minimal-risk research activity prior to seeking a full authorization from research participants.
- Methods for identifying individuals may include the following:
 - Reviewing medical charts
 - Reviewing databases that include PHI
 - Reviewing other medical- or health-based documents that include PHI
- Identifiable information used under this waiver may include the following, as this is the minimum necessary for identifying eligible individuals:
 - Name
 - Contact information, such as phone number, address, or email address
 - An ID number, such as MRN or SSN
 - Date of birth
 - Medical and health information that may determine study eligibility
- Any PHI recorded by the study team will only be used for recruitment and determining study eligibility. After this has been completed, the PHI must be removed from the research record or destroyed, unless the participants have given authorization for continued use of the PHI.
- PHI will only be viewed by approved members of the study team and will not be disclosed for research purposes to any individual or institution without the participants' authorization for such use and disclosure of the PHI.
- PHI will be stored in a secure manner according to HIPAA privacy and security provisions.

IRB_00086498

Created: 9/19/2015 4:57 PM

PI: [name]

Submitted: 3/29/2016

Title: Spectacle Tints and Thin-Films to Reduce Headache Frequency
in Patients with Migraine

Investigational Use of a Device

1. What is the initial risk determination of the device study according to the investigator and/or sponsor?

The study is a non-significant risk (NSR) device study.

a. Provide IDE (or HDE) Number(s) for significant risk devices:

IDE #	Device Name	IDE Holder
There are no items to display		

b. Attach verification of the IDE number for significant risk devices to the Documents and attachments page. Please check the method by which you choose to verify the IDE number:

There are no items to display

2. Describe the plan to control, store, and dispense the investigational device. This plan should ensure that the device is only used by qualified investigator(s) for the participants enrolled in this research project.

The following label will be affixed to the inside of case for the glasses:

Axon Optics, LLC, Salt Lake City, UT, USA

CAUTION: Investigational device. Limited by Federal law to investigational use. Not suitable for night driving.

Thin film coatings for spectacles are similar in design to anti-reflective coatings commonly dispensed for prescription and cosmetic eyewear. Anti-reflective coatings may be purchased without a prescription. There are no known risks to subjects from anti-reflective or other thin-film coatings. In a previous study of thin-film coatings and migraine, there were no adverse effects of the coatings. The tinted spectacles used in this study will be similar to non-prescription eyewear one could purchase without a prescription. However, because the study lenses are part of an investigational medical device study, all spectacle frames that contain study lenses will be numbered and stored in a locked cabinet. Only the research team at each site will have access to lenses and the research team will use an Excel log to track the location of all study lenses.

IRB_00086498**Created:** 9/19/2015 4:57 PM**PI:** [name]**Submitted:** 3/29/2016**Title:** Spectacle Tints and Thin-Films to Reduce Headache Frequency in Patients with Migraine

Non-Significant Risk Device

Review the following definition of a non-significant risk (NSR) device:

1. The medical device is not a significant risk device, because all of the following are true:
 - a. The medical device is NOT intended as an implant that presents a potential for serious risk to the health, safety, or welfare of a subject.
 - b. The medical device is NOT purported or represented to be for a use in supporting or sustaining human life that presents a potential for serious risk to the health, safety, or welfare of a subject.
 - c. The medical device is NOT for a use of substantial importance in diagnosing, curing, mitigating, or treating disease, or otherwise preventing impairment of human health that presents a potential for serious risk to the health, safety, or welfare of a subject.
 - d. The medical device is does NOT otherwise present a potential for serious risk to the health, safety, or welfare of a subject.
2. The medical device is not banned.

1. **Provide justification of why the investigational medical device used in this study meets the definition of a NSR device.**

Spectacle lenses are considered to be 510(K) exempt according to this page from FDA:

<https://www.accessdata.fda.gov/scripts/cdrh/cfdocs/cfPCD/classification.cfm?ID=HQG>

(accessed 20-March-2018). The product classification and the page from CFR 21 are attached to this application.

IRB_00086498

Created: 9/19/2015 4:57 PM

PI: [name]

Submitted: 3/29/2016

Title: Spectacle Tints and Thin-Films to Reduce Headache Frequency in Patients with Migraine

8. Resources and Responsibilities

1. State and justify the qualifications of the study staff:

The principal investigator will be responsible for the design and execution of the study. The PI is a board-certified ophthalmologist and has been responsible for the safe conduct of other trials at the University. He has completed all required CITI training.

Site Investigators will be responsible for subject recruitment and the safe conduct of the study at each site. All investigators will be board certified or board eligible neurologists, familiar with the treatment of migraine and other headache disorders..

Site Study Coordinators will be responsible for insuring that subjects meet all inclusion and exclusion criteria, that subjects provide informed consent, that subjects complete all study instruments and that subjects comply with the study protocol. They will also be responsible for data entry and maintenance of subject and regulatory binders. They will be responsible for reporting adverse events.

The CRO will be responsible for qualifying study sites, and periodically auditing the sites for compliance with study protocol.

The CRO will insure that all site personnel have undergone appropriate training for their role, that they've completed appropriate training in the safe conduct of human clinical research, and that they have completed appropriate training in good clinical practice.

2. Describe the training that study staff and investigators will receive in order to be informed about the protocol and understand their research-related duties and functions:

The PI at each site will be asked to sign the protocol document indicating that they have read, that they understand, and that they will comply with the protocol.

The CRO or [name] will conduct a teleconference with the research team at each site before they begin enrollment to insure they understand the protocol and to answer questions they may have about study procedures.

The CRO will maintain a training log that documents that the research team at each site has completed appropriate training in the conduct of human research.

The CRO will conduct periodic audits of each site to insure that regulatory binders are up-to-date.

3. Describe the facilities where the research activities will be performed (e.g. hospitals, clinics, laboratories, classrooms/schools, offices, tissue banks, etc.).

All research activities will be conducted at an outpatient clinic.

Other sites collaborating in this research include:

Mayo Clinics, Scottsdale, AZ. Site PI: [name]

Northwell Health/Hofstra University, Great Neck, NY. Site PI: [name]

Brigham and Women's Hospital/Harvard University, Boston, MA. Site PI: [name]

University of Texas Southwestern, Dallas, TX. Site PI: [name]

Each of these sites are governed by their local IRB.

4. Describe the medical or psychological resources available at this site (and other participating sites, if applicable) that participants might require as a consequence of the research. If not applicable, please state.

All subjects will already be under the care of a physician for their headaches. Because the study is not anticipated to incur any additional risk to subjects, no specific additional resources will be made available to subjects.

IRB_00086498**Created:** 9/19/2015 4:57 PM**PI:** [name]**Submitted:** 3/29/2016**Title:** Spectacle Tints and Thin-Films to Reduce Headache Frequency
in Patients with Migraine

Documents and Attachments

If any of your documents (such as investigational brochures, sponsor protocols, advertisements, etc.) are not available in an electronic format, please scan and save them as PDF files or contact our office for assistance.

Naming Documents: Please use the title field to clearly indicate the content of each form. The name you enter will be listed on your approval letter. Use names that will differentiate from earlier versions.

Examples:

Consent Document Control Group 04/14/05

Consent Document Treatment Group 4/14/05

Sponsor Protocol 04/14/05 Version 2

Assent Document(Highlighted Changes)

[Apple/Macintosh Users:MS Word documents must have a .doc file extension. See ERICA home page for instructions.](#)

